#### **Outcome measurement**

The primary outcome measured will be the ADR, defined as the proportion of subjects with at least one traditional adenoma (including tubular or villous adenomas, and adenomas with high grade dysplasia or adenocarcinoma) of any size. Secondary outcomes measured included the adenomas per colonoscopy (APC), serrated adenoma detection rate (SDR), defined as the proportion of subjects with at least one serrated polyp (serrated adenoma or traditional serrated

adenoma) of any size as well as the neoplasia detection rate (NDR), defined as the percentage of colonoscopies in which at least one traditional adenoma or serrated adenoma was found. Additionally, the location, size, morphology and number of polyps will also be recorded. Flat polyps will be defined as flat appearing polyps, in which the height was less than two times the diameter. Histology of polyps will be evaluated by expert gastrointestinal pathologists at UCSF, who will be blinded to the specific endoscopic diagnosis and the histopathological diagnosis was used as the gold-standard. High risk adenomas will be defined as an adenoma of any size with high grade dysplasia or a villous component, an adenoma greater than ten millimeters in size, adenocarcinoma, and, or three or more adenomas of any size found on a single colonoscopy.

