#### Randomization

Patients will be randomized (1:1) to HDWL alone or i-scan 1 during colonoscopy. The randomization order will be determined by using a computer-generated sequence in block sizes of 30. Sealed, opaque envelopes containing the randomization assignment will be prepared by one investigator. After obtaining informed consent from the patient, the envelope will be opened to reveal the randomization assignment prior to beginning the procedure.

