### Colonoscopy procedure

All patients will need to complete a bowel preparation using split-dose US Food and Drug Administration-approved preparations. Four attending physicians, each of whom performed over 500 colonoscopies the year prior, will perform withdrawal in every procedure. Insertion of the colonoscope and withdrawal from cecum will be performed with the assigned imaging modality (i.e., HDWL or i-scan 1). The i-scan 1 setting that will be used will be the "out of the box" setting (supplementary table) that is standard with Pentax colonoscopes (Pentax EC-3890 and EC-3490); no adjustments will be made to the setting. If a lesion/polyp were detected, the physician will be permitted to change from i-scan 1 to HDWL and vice versa at their discretion to interrogate and better characterize the lesion/polyp per their routine practice. Once the lesion/polyp is removed and retrieved, the physician can return to the assigned imaging modality for inspection. Withdrawal time will be measured from the time withdrawal from the cecum began to the end of the examination – the time will not be "paused" for polyp resection. Withdrawal time during a negative colonoscopy exam (one in which no polyps were identified and no interventions were performed), called the "negative withdrawal time," will also be separately analyzed. Resected polyps will be sent for pathologic examination as part of routine clinical care.

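### Does the plan need to say that the pathologists are masked to the imaging arm as well as to the endoscopic diagnosis?

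*Combined protocol and SAP*

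**What the plan says.** Under Outcome measurement, the primary endpoint is fixed in these words: "The primary outcome measured will be the ADR, defined as the proportion of subjects with at least one traditional adenoma". The same section says who makes the call: "Histology of polyps will be evaluated by expert gastrointestinal pathologists at UCSF". Its one statement on blinding describes these readers as people "who will be blinded to the specific endoscopic diagnosis and the histopathological diagnosis was used as the gold-standard". No central or second read is described.

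Two other sections bear on what the pathologists could know. Under Randomization, "the envelope will be opened to reveal the randomization assignment prior to beginning the procedure", so the procedure room knows the arm from the start. Under Colonoscopy procedure, "Resected polyps will be sent for pathologic examination as part of routine clinical care", with nothing on what the specimen request should show or leave out. That section also lets the operator change modes once a lesion is found: "the physician will be permitted to change from i-scan 1 to HDWL and vice versa at their discretion".

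No section states that pathologists are masked to the arm, and no section states that they are told it.

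**The concern.** Not knowing the endoscopic diagnosis is different from not knowing the arm. A pathologist could be unaware that a polyp was judged hyperplastic and still know that the patient was examined with i-scan. The concealed envelopes protect allocation only until they are opened; they do nothing for outcome assessment afterwards. Read literally, a specimen request naming the arm would not breach the protocol.

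The endpoint makes this worth asking. For a patient with resected tissue, the pathologist's adenoma call decides whether that patient counts towards ADR. The operator cannot be masked, so histology is the step of outcome assessment where masking is feasible. If readers knew the arm and leaned towards adenoma for i-scan specimens, the trial could show a difference with no true gain in detection, and type I error would exceed the nominal 5%. Serrated versus hyperplastic calls could move the serrated and neoplasia detection rates but not ADR.

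**Working it through.** **1. The plan's own figure.** Inputs from Sample size and statistical analysis: control ADR 30%, difference 10 points (so 40%), two-sided 5% error, 80% power. With pooled variance under the null and no continuity correction:

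n = [1.960 × √(2 × 0.35 × 0.65) + 0.842 × √(0.30 × 0.70 + 0.40 × 0.60)]² / 0.10² = (1.322 + 0.565)² / 0.01 ≈ 356 per group.

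This matches the stated 356. Masking does not enter the calculation, so the sample size is not at issue.

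**2. Who could be misclassified.** A patient with a true adenoma already counts, and a patient with nothing resected cannot be upgraded. Only patients with resected tissue and no adenoma can be moved into the ADR numerator. The documents give neither their share nor a misreading rate, so both are assumed:

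- s = share of non-adenoma patients with resected tissue, 0.30 to 0.50;
- m = proportion of those falsely upgraded, in the i-scan arm only, 2% to 10%.

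**3. Bias.** With true ADR 30% in both arms, false difference d = 0.70 × s × m, and extra patients = 356 × d.

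**4. Type I error.** With p₂ = 0.30 + d and p̄ = 0.30 + d/2, SE₀ = √(2p̄(1 − p̄)/356) and SE₁ = √((0.21 + p₂(1 − p₂))/356). The two-sided rejection probability is Φ((d − 1.96 SE₀)/SE₁) + Φ((−d − 1.96 SE₀)/SE₁).

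| m | s | d (points) | extra patients | type I error |
|---|---|---|---|---|
| 2% | 0.30 | 0.42 | 1.5 | 5.2% |
| 2% | 0.50 | 0.70 | 2.5 | 5.5% |
| 5% | 0.30 | 1.05 | 3.7 | 6.1% |
| 5% | 0.50 | 1.75 | 6.2 | 8.0% |
| 10% | 0.30 | 2.10 | 7.5 | 9.3% |
| 10% | 0.50 | 3.50 | 12.5 | 17.1% |

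Bottom row in full: p₂ = 0.335, SE₀ = 0.0349, SE₁ = 0.0349; the upper tail is Φ(−0.96) ≈ 0.169, the lower tail about 0.0015, total 0.171. Exact binomial enumeration of the uncorrected χ² test agrees with every row to within 0.03 percentage points and gives 5.02% with no upgrading.

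**5. Scale.** The standard error of the ADR difference under the null is √(2 × 0.30 × 0.70/356) = 0.0343, or 3.4 points. A bias of 0.4 to 0.7 points is between about one eighth and one fifth of that.

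**6. What m contains.** The model applies m to every eligible i-scan patient, so m is a product: the chance that the pathologist knows the arm, times the chance that this knowledge turns a non-adenoma into an adenoma. If the arm were known for half the specimens, a 5% overcall among those would give m = 2.5% and d = 0.53 to 0.88 points.

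**7. Reading the sections together.** A specimen sent through routine care need not carry a research allocation, and the protocol does not say that it does. Because operators may switch modes to characterise a lesion, a mention of i-scan against one polyp would not by itself reveal the arm.

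**The case for a change.** The best case for a change is that it is nearly free and cannot be made later. A phrase in the protocol and an instruction on specimen requests would settle the matter without new readers, slides or patients, and once histology has been signed out with the arm visible, masking cannot be restored. The trial team evidently thought it worth blinding these readers, yet specified the blind for the endoscopic diagnosis and not for the comparison under test. At the top of both assumed ranges, type I error is 17.1%.

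Much of this stands as good practice. The statement is incomplete, and a report that could say histology was read masked to arm would be stronger. It does not show that the plan as written yields an unsound result. The 17.1% needs three things together: pathologists who learn the arm, who favour i-scan, and who overcall in that arm only, at 10% of all eligible patients with the larger tissue share. The documents support none of these. Low cost makes an edit harmless; it does not turn a silence into a defect. Nor would it touch the larger exposure, which is that the operator knows the arm and controls inspection and resection.

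**Conclusion.** No change follows. The protocol leaves a detail unstated: it blinds pathologists to the endoscopic diagnosis and is silent on the arm. Nothing in it shows that they would learn the arm, and the blind it does specify removes the cue most likely to sway the reading of an individual polyp. The arm alone says little about the histology of a given specimen.

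The effect on ADR cannot be estimated from the documents and is probably small: at a 2% one-sided upgrade rate it is 0.4 to 0.7 points, or 1.5 to 2.5 patients in 356, with type I error of 5.2% to 5.5%. All such figures rest on an assumed tissue share and upgrade rate and are illustrative. If it emerged that the arm was routinely visible to pathology, that would belong among the limitations when the trial is reported. Followed as written, and as far as the documents show, the plan still gives a sound comparison of ADR between arms.

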# Sample size and statistical analysis

The sample size calculation for the primary outcome of ADR was based on the average ADR of our group over the previous two years of 30%, which we estimated would be the control (HDWL) group's ADR. We estimated a 10% difference between groups based on a previous study. To achieve an absolute difference of 10% in the ADR between groups with a statistical type I error of 5% (two-sided) and power of 80%, a minimum of 356 patients per group was needed (712 patients total). Adjusting for a 4% drop-out due to bowel prep or inability to intubate the cecum, we targeted enrollment of 740 patients.

Intention-to-treat analysis will be used to assess the primary and secondary outcomes. We will also perform per-protocol analyses to explore differences in the primary and secondary outcomes after excluding patients with preparations that were considered too difficult to correct with intraprocedural washing (i.e., Boston bowel prep score < 2 in any segment). Only patients with a complete procedure and adequate bowel preparation will be included in the per-protocol analyses. Categorical data will be compared by the  $\chi^2$ -test or Fisher Exact test where appropriate

and numerical data will be compared by the Student's t-test. Statistical significance will be defined as a two-sided p-value < 0.05.

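### Does the unstated unit of analysis for polyp location, size and morphology make the planned tests invalid?

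*Combined protocol and SAP*

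**What the plan says.** Under Outcome measurement, the combined protocol and SAP names ADR as the primary outcome and APC, SDR and NDR as secondary outcomes. Each is defined per subject or per colonoscopy. The section then adds that "the location, size, morphology and number of polyps will also be recorded". It gives a working definition of one morphology class ("Flat polyps will be defined as flat appearing polyps") and counts "three or more adenomas of any size found on a single colonoscopy" among the criteria for high risk adenomas.

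Under Sample size and statistical analysis, the intention-to-treat and per-protocol analyses are tied to the primary and secondary outcomes. One general rule on tests follows: "Categorical data will be compared by the" chi-square test, or Fisher's exact test where appropriate, and "numerical data will be compared by the" Student's t-test. The threshold is also general: "Statistical significance will be defined as a two-sided p-value < 0.05".

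Neither section gives a unit of analysis for polyp location, size or morphology. Neither mentions a per-patient summary, a GEE or mixed model, a clustered variance, or a purely descriptive role for these features.

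**The concern.** Patients are randomised, but location, size and morphology belong to individual polyps, and the plan itself expects some patients to have several. The only tests named assume independent observations. If all polyps in an arm were pooled and tested that way, positive within-patient correlation would make the standard errors too small and the p-values too low.

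An enhanced-imaging trial invites such a comparison, for instance of the share of flat or proximal polyps between arms. A chance difference there could be reported as significant. With the unit unwritten, it could also be chosen after the data are seen.

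**Working it through.** **1. The plan's own figure.** Inputs from Sample size and statistical analysis: 30% against 40%, two-sided 5%, power 80%. With pooled variance and no continuity correction:

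n = [1.96·√(2·0.35·0.65) + 0.8416·√(0.30·0.70 + 0.40·0.60)]² / 0.10² = (1.3221 + 0.5646)² / 0.01 ≈ 356 per group.

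This matches the stated 356 (712 in total). Allowing for 4% drop-out gives 712/0.96 = 742 against the stated 740, a trivial difference. The calculation counts patients and concerns ADR, so polyp clustering does not enter it.

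**2. What pooling would do.** If m is the size-weighted mean number of polyps per polyp-bearing patient, the variance is understated by the design effect DE = 1 + (m − 1)·ICC. The true error of a nominal 5% test is then 2·[1 − Φ(1.96/√DE)]. The documents give neither m nor the ICC, so both are assumptions.

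- m = 2.59, ICC 0.1: DE = 1 + 1.59·0.1 = 1.16; true error 6.9%.
- m = 3.69, ICC 0.3: DE = 1 + 2.69·0.3 = 1.81; true error 14.5%.
- ICC 0, or one polyp per patient: DE = 1; true error 5%.

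**3. First simulation under the null.** 370 patients per arm (740/2) and 10,000 trials per cell. Counts were negative binomial (mean 0.6 with k = 0.6, or mean 1.2 with k = 0.8). The binary feature had prevalence 0.3; size was lognormal with median 5 mm and log SD 0.5.

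| Pooled test | Mean polyps per patient | ICC 0.1 | ICC 0.2 | ICC 0.3 |
|---|---|---|---|---|
| Chi-square | 0.6 | 6.7% | 8.6% | 10.2% |
| Chi-square | 1.2 | 8.3% | 11.8% | 14.8% |
| t-test on size | 0.6 | 6.3% | 8.6% | 10.3% |
| t-test on size | 1.2 | 7.9% | 10.7% | 13.5% |

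At ICC 0 both pooled tests gave 4.9–5.0%. A patient-level chi-square on having at least one polyp with the feature gave 4.6–5.3%. A polyp-level test with patient-clustered variance gave 4.9–5.7%.

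**4. Second simulation, different count model.** 370 patients per arm, half of them with polyps, one plus a geometric number of polyps each. There were 4,000 trials per cell, fewer for Fisher.

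| Mean polyps per polyp-bearing patient | ICC | Chi-square | t-test | Fisher |
|---|---|---|---|---|
| 1.5 | 0.1 | 6.7% | 5.9% | 5.9% |
| 1.5 | 0.3 | 9.3% | 8.2% | 8.7% |
| 2.0 | 0.1 | 7.0% | 7.3% | 6.0% |
| 2.0 | 0.3 | 12.2% | 12.1% | 11.2% |
| 2.5 | 0.1 | 9.1% | 8.8% | 7.7% |
| 2.5 | 0.3 | 16.3% | 15.2% | 16.7% |

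At ICC 0 the rates were 4.0–5.9%. At mean 2.0 the formula agrees: the count variance is 1·(1 + 1) = 2, so m = (2² + 2)/2 = 3, and DE = 1.2 and 1.6 give 7.4% and 12.1%.

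**5. Which conditions the plan supplies.** Inflation needs four things together:

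- *Several polyps in some patients.* Supplied, by the high risk adenoma definition.
- *A between-arm test on these features.* Not stated. They are listed as recorded, after the named outcomes. By contrast, the Colonoscopy procedure section says explicitly that negative withdrawal time will be analysed.
- *The polyp as unit, treated as independent.* Not stated. Randomisation, sample size and every named outcome use the patient or the colonoscopy.
- *Positive within-patient correlation of the feature.* Not given.

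The general test rule does not need polyps to have a purpose. ADR, SDR and NDR are categorical per patient; APC and the withdrawal times are numerical per patient.

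**The case for a change.** The strongest case for a change is that the test rule is unrestricted and flat polyps are given an operational definition, which suggests they will be tabulated by arm. The high risk adenoma definition also mixes lesion criteria with a per-colonoscopy count, so the two units are not kept strictly apart. Two or three sentences would settle the matter without touching sample size or data collection, and the inflation appears under two different count models.

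Much of this stands. The unit is unwritten, and pooling correlated polyps would be wrong. But expecting several lesions in a patient is not a plan to pool them, and a tabulation by arm needs no p-value. That the unit could be chosen later is true of any exploratory summary left unspecified, and it cannot reach the primary conclusion.

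Nor is the added text a plain gain. Having at least one flat polyp, over all randomised patients, is a detection rate; it answers a different question from the mix of polyps found. A polyp-level model with clustered variance corrects the standard error, with intervals wider by √1.16 to √1.81, or about 8% to 34%. It still conditions on detection, which the imaging mode may itself affect, and both simulations used the same count distribution in the two arms, so they do not test that.

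**Conclusion.** The gap is real but needs no change to the plan. Followed as written, the plan analyses its primary and secondary outcomes with patients or colonoscopies as units, where clustering of polyps within patients does not arise. The effect on ADR, APC, SDR, NDR and the 356 per group is nil.

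The possible harm is confined to exploratory p-values on recorded descriptors that the plan does not commit to producing. If an analyst did pool polyps, the true error at a nominal 5% would be about 6% to 17% for ICC 0.1 to 0.3, with no systematic excess at ICC 0. Those figures rest wholly on assumed polyp counts, feature distributions and ICCs, and serve only as illustration. A competent analyst would describe these features, summarise them per patient or allow for clustering, and each course is compatible with the present text.

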# **Study eligibility**

Patients will be recruited between February 1, 2017 and December 31, 2017. Inclusion criteria included patients ages 50 to 75 years who were scheduled for outpatient colonoscopy for the indications of CRC screening, post-polypectomy surveillance, or diagnostic workup for a positive fecal-based test (FIT). Exclusion criteria were inpatients and patients with inflammatory bowel disease, colorectal cancer, polyposis syndromes, previous surgical resection of any portion of the colon or rectum, and patients referred for endoscopic mucosal resection of previously diagnosed colorectal polyps.

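### Optional low-cost improvement, not an error: the primary ADR analysis could be pre-specified as stratified by colonoscopy indication, changing power by about -0.2 to +1.3 points under assumed spreads

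*Combined protocol and SAP*

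**What the plan says.** The analysis text under Sample size and statistical analysis gives one rule for all categorical data, and so for ADR: a chi-square "test or Fisher Exact test where appropriate". It names no covariate, no stratum, no effect estimate and no confidence interval for ADR. The control rate is "based on the average ADR of our group over the previous two years of 30" per cent, one pooled figure. The population is set by "Intention-to-treat analysis will be used to assess the primary and secondary outcomes", and the target by "Adjusting for a 4% drop-out due to bowel prep or inability to intubate the cecum, we targeted enrollment of 740 patients".

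Under Randomization, "The randomization order will be determined by using a computer-generated sequence in block sizes of 30"; no stratification factor is named. On timing, "After obtaining informed consent from the patient, the envelope will be opened to reveal the randomization assignment prior to beginning the procedure".

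Two possible baseline factors appear elsewhere. Study eligibility admits three indications: "CRC screening, post-polypectomy surveillance, or diagnostic workup for a positive fecal-based test (FIT". Colonoscopy procedure states: "Four attending physicians, each of whom performed over 500 colonoscopies the year prior, will perform withdrawal in every procedure". Neither section gives ADR, case mix or caseload by indication or by endoscopist, and nothing says whether the endoscopist is settled before allocation is revealed.

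**The concern.** The trial is sized at exactly 80% power, so precision available without extra patients is worth considering. If ADR differs by indication, a comparison made within indications removes that variation from the standard error. The crude test leaves it in.

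Only efficiency is at stake. The crude test keeps its type I error, and it matches both the unstratified allocation and the two-proportion sample-size calculation. Timing matters because an adjusted estimate carries most weight when it is fixed before outcomes are seen.

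**Working it through.** **1. The plan's own figure.** Inputs from Sample size and statistical analysis: ADR 0.30 against 0.40, two-sided 5%, power 80%. With mean rate 0.35 and pooled variance under the null:

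n = [1.960 × √(2 × 0.35 × 0.65) + 0.8416 × √(0.30 × 0.70 + 0.40 × 0.60)]² / 0.10²
= [1.960 × √0.455 + 0.8416 × √0.450]² / 0.01 = 355.9, so 356 per group.

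This matches the plan. Power is 80.0% at 356 per group. At 740 / 2 = 370 per group it is 81.5%, if every enrolled patient contributes an outcome.

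**2. What stratification does.** For strata with shares w and rates p0 and p1, the stratified analysis replaces 0.450 by V1 = Σ w[p0(1 - p0) + p1(1 - p1)], and 0.455 by V0 = 2 Σ w p̄(1 - p̄), where p̄ is the mean of p0 and p1. Take the strongest spread in the main set: mix 60/30/10% and odds ratios 1/2/3, both assumed, with one treatment odds ratio across strata and overall rates held at 30% and 40%.

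- Control rates: 0.232, 0.377, 0.476. Check: 0.6 × 0.232 + 0.3 × 0.377 + 0.1 × 0.476 = 0.300.
- i-scan rates: 0.324, 0.489, 0.590. Check: 0.6 × 0.324 + 0.3 × 0.489 + 0.1 × 0.590 = 0.400.
- Control variance: 0.6 × 0.232 × 0.768 + 0.3 × 0.377 × 0.623 + 0.1 × 0.476 × 0.524 = 0.202. The same sum for i-scan is 0.231. So V1 = 0.433 and, in the same way, V0 = 0.438.
- Power = Φ{[0.10 - 1.960 × √(0.438 / 356)] / √(0.433 / 356)} = Φ(0.896) = 81.5%.

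That is about 1.5 points above 80.0%. The formula ignores the small cost of splitting the sample, so simulation is needed for the net change.

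**3. Simulation, indication alone.** 712 patients, unstratified allocation, uncorrected chi-square against the Cochran-Mantel-Haenszel test, 50,000 to 200,000 trials per scenario with an effect. The Monte Carlo standard error of each difference is about 0.02 to 0.12 points.

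| Indication odds ratios | Change in power (points) |
|---|---|
| 1/1/1 | -0.2 to 0.0 |
| 1/1.2/1.45 | -0.2 to 0.0 |
| 1/1.5/2 | +0.4 to +0.5 |
| 1/1.5/2.5 | +0.6 to +0.8 |
| 1/2/3 | +1.1 to +1.3 |

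Type I error is 4.8 to 5.2%. In the last three rows the ratio of Mantel-Haenszel to crude variance is about 0.990, 0.981 and 0.967. Saving that share of 712 patients gives 712 × 0.010 ≈ 7, 712 × 0.019 ≈ 14 and 712 × 0.033 ≈ 23. The upper end moves with the assumption: control ADRs of 20/35/50% (odds ratios about 1/2.2/4) with a 45/40/15% mix give +1.9 points.

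**4. Adding endoscopist (3 × 4 = 12 strata).**

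| Endoscopist ADR; indication odds ratios | Change in power (points) |
|---|---|
| All 30%; 1/1/1 | -0.8 to -0.7 |
| 26-34%; 1/1.2/1.45 | -0.6 to -0.4 |
| 25-35%; 1/1.5/2 | about 0 to +0.2 |
| 20-40%; 1/1.5/2.5 | +0.9 to +1.6 |
| 15-45%; 1/2/3 | +2.6 to +3.3 |

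Within a row, results depend on how caseloads and the two middle endoscopist rates are set. Strata also thin out. With 10% FIT patients and equal caseloads, each endoscopist's FIT stratum expects 712 × 0.10 × 0.25 = 17.8 patients. An endoscopist with 5% of cases would have 712 × 0.10 × 0.05 = 3.6. With indication alone, the smallest stratum expects 712 × 0.10 = 71.2.

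**The case against.** The strongest reply is that this is preference. The planned test is valid, agrees with the sample-size calculation and omits no design factor, because allocation is unstratified. The only relevant rate in the documents is the pooled 30%, so every gain comes from assumed spreads. The range for indication includes small losses, and its top is less than the 1.5 points already obtained by going from 356 to 370 per group (81.5 - 80.0).

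Most of this stands, and it is why the point is optional. It does not dispose of stratifying by indication. That is a concrete method using a value known before allocation, it loses at most about 0.2 points in the scenarios examined, and its gain comes on top of that from enrolling 740.

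The objection succeeds against endoscopist. Two factors lose power even when both predict ADR weakly. Larger gains need a spread such as 15-45%, and the documents give neither that spread nor the timing of endoscopist assignment.

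A reader might also infer that the crude analysis is biased or underpowered because indication or endoscopist could be unbalanced by chance. The documents do not support this. Chance imbalance under randomisation is already covered by the crude standard error, and 356 per group delivers the stated power without adjustment.

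**Conclusion.** The point holds as an optional efficiency improvement, not a correction. With a 60/30/10% mix and odds ratios between 1/1/1 and 1/2/3, stratifying by indication changes power at 712 patients by about -0.2 to +1.3 points, with type I error near 5%. The change is about zero if indication predicts ADR only weakly, and the gain could be somewhat larger if its effect is stronger than assumed. These figures mean little without their assumptions, since the documents report no ADR or case mix by indication.

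A gain of about 3 points from adding endoscopist is tempting to quote. It should not be: it needs the widest spread considered and an assignment fixed before the envelope is opened, and neither is documented.

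**What to change.** Before outcome data are seen, state that the primary ADR comparison is a Cochran-Mantel-Haenszel test with a Mantel-Haenszel risk difference and 95% confidence interval, stratified by the three indications. Say that the difference is read as a weighted average across strata. This stays on the absolute scale used for the sample size and supplies the estimate and interval that the plan does not name. Keep the crude chi-square as a sensitivity analysis.

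The protocol mixes past and future tense, so its timing is unclear. If outcomes have already been seen, leave the crude test as primary and label the stratified analysis supportive.

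Use endoscopist only in a secondary or sensitivity analysis, and only if recorded before the envelope is opened. In that case fix a merging rule for sparse strata in advance, based on counts without outcomes. If the two-year data behind the 30% can be split by indication, they would show whether a gain is plausible.

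The cost is a few lines of text, one recorded variable and a slightly longer analysis. It needs no extra patients and no change to randomisation. The price is about 0.1 to 0.2 points of power if indication does not predict ADR.
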